#### **5. Health Related Quality of life:**

Using the Arabic SF-36 (**Appendix IV**), Patients will be asked to fill out the questionnaire (tick boxes) by themselves and then it is scored by a clinician or researcher (**El-Kalla, 2016**).

#### **6. Fear of movement**

Using the Arabic Tampa (**Appendix V**), Patients will be asked about any excessive, irrational, and debilitating fear of physical movement and activity resulting from a feeling of vulnerability to painful injury or re-injury (**Al-Shudifat et al., 2020**).

#### **7. Adherence**

Individuals will be followed in a checklist at each session with the date of the session. The absence of the participant for two sessions will lead to consideration of being drop out.

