### Sample Size Calculation:

A priori power analysis for ANOVA, repeated measures, within-between interactions was used with an effect size of 0.28, alpha level ( $\alpha$ ) = 0.05, and power ( $1-\beta$ ) = 0.95. The estimated sample size required was 54 participants, which was increased to account for potential dropouts as shown in **(Figure 1)**. Thus, the total sample will include 60 participants, randomly allocated into 3 equal groups (n= 20 per group).

Sample size was calculated using G\*Power software version 3.1.9.7, referencing effect size data of pain severity from a recent study studying the effects of thoracic and hip joint mobility exercise with lumbar stabilization exercise on pain and balance **(Choi and Kim, 2023)**.

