#### **Treatment Procedures:**

- The control group (n=20) will receive core stabilization (3 sessions/ week for 6 weeks)
- The 1st experimental group (n=20) will receive core stabilization in addition to thoracic mobility exercises (3 sessions/ week for 6 weeks)
- The 2nd experimental group (n=20) will receive core stabilization in addition to hip mobility exercises (3 sessions/ week for 6 weeks).
- Adherence will be monitored using attendance logs and exercise checklists.
- Any adverse effects or symptom exacerbation will be recorded.

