**Figure (9): Hip Mobility Exercises. (Demirtas et al., 2023)**

### **Data analysis and statistical design**

Statistical analysis will be performed using SPSS software for Windows, version 25.0 (SPSS, Inc., Chicago, IL) with Alpha level set at 0.05.

- Data will be screened for normality assumption, homogeneity of variance, and presence of extreme scores.
- Descriptive statistics will be calculated for all groups at baseline and after 6 weeks.
- ANOVA, repeated measures, within-between interactions model will be utilized to determine any differences between the mean change scores of groups regarding all outcomes.
- Bonferroni adjusted p-values for every outcome measure to protect against the possibility of type I error.

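### The two-absence rule lets attendance decide who counts as a drop-out, which risks discretionary exclusion after randomisation and could use up the six-patient allowance

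*Protocol*

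**What the plan says.** Four parts of Chapter III of the protocol bear on this.

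- **Assessment Procedures, 7. Adherence.** Attendance is logged at each session, and then: "The absence of the participant for two sessions will lead to consideration of being drop out". The text does not say whether the two absences are cumulative or consecutive, whether an excused or made-up session counts, or who decides and on what criteria.
- **Treatment Procedures.** The control group "will receive core stabilization (3 sessions/ week for 6 weeks"), and both experimental groups follow the same timetable with exercises added.
- **Sample Size Calculation.** "The estimated sample size required was 54 participants, which was increased to account for potential dropouts". As a result, "the total sample will include 60 participants, randomly allocated into 3 equal groups (n= 20 per group").
- **Data analysis and statistical design.** "ANOVA, repeated measures, within-between interactions model will be utilized to determine any differences between the mean change scores of groups regarding all outcomes". Assessments are at baseline and after 6 weeks, so each patient has two time points.

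Nothing in the protocol says that a patient considered a drop-out for missed sessions is still assessed at week 6 or kept in the analysis. Nothing says that such a patient is removed from either.

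**The concern.** Missing treatment sessions and being lost to follow-up are different events, and the rule merges them. A patient with two absences may be available and willing at week 6. Labelling that patient a drop-out puts them in the category that the sample-size section counts as lost.

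Attendance is observed after randomisation. It can depend on pain, on response (the protocol expects some symptom exacerbation and plans to record it) and on how demanding the programme is. All three arms share the core programme; arm B adds six thoracic exercises and arm C adds eight hip exercises. If patients are removed for absence, and either the frequency of absence or its relation to response differs between arms, the groups compared are no longer those created by randomisation. Because the wording leaves the decision open, case-by-case judgement could add to the problem.

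The second issue is numbers. The margin between 54 and 60 is six patients, and a trigger set at two absences could use it up before any true loss to follow-up.

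**Working it through.** **Inputs from the protocol.** Sessions: 3 × 6 = 18. Trigger: 2 absences, i.e. 2/18 = 11.1% missed and 16/18 = 88.9% attended. "effect size of 0.28", "Alpha level set at 0.05", target power 0.95, three groups, two time points, required N = 54, randomised N = 60. The implied allowance is 60 − 54 = 6, or 6/60 = 10%; the protocol states no percentage.

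**Assumed inputs.** Correlation between baseline and week 6: r = 0.5 (not in the text). Absence per session: 2% to 10%, independent between sessions (no rate is given).

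**Step 1: reproduce the plan's figure.** For the within-between interaction, λ = N·f²·m/(1 − r), df1 = (k − 1)(m − 1), df2 = (N − k)(m − 1), with k = 3 and m = 2. At N = 54, λ = 54 × 0.0784 × 2/0.5 = 16.9 with 2 and 51 df, giving power 0.956. The smallest N in equal groups reaching 0.95 is 54, and 54/0.90 = 60. The stated design reproduces at r = 0.5. At r = 0, 0.3 and 0.7 the required N would be 102, 75 and 33.

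**Step 2: cumulative reading.** P(at least 2 of 18 missed) = 1 − (1 − p)^18 − 18p(1 − p)^17. At p = 0.05 this is 1 − 0.3972 − 0.3763 = 0.2265.

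| Absence per session | P(trigger) | Expected of 60 | Left | P(more than 6) | Power if all are excluded |
|---|---|---|---|---|---|
| 2% | 0.0495 | 3.0 | 57.0 | 0.03 | 0.966 |
| 3% | 0.1003 | 6.0 | 54.0 | 0.40 | 0.956 |
| 4% | 0.1607 | 9.6 | 50.4 | 0.87 | 0.941 |
| 5% | 0.2265 | 13.6 | 46.4 | 0.99 | 0.920 |
| 10% | 0.5497 | 33.0 | 27.0 | 1.00 | 0.685 |

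P(trigger) is exactly 10% at p = 2.99%. At a whole-number N of 46 the power is 0.917.

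**Step 3: consecutive reading.** If two absences in a row are needed, expected labels among 60 are 0.9 at 3%, 2.4 at 5%, 8.7 at 10% and 17.5 at 15%. The allowance of 6 is therefore passed somewhere between 5% and 10%.

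**Step 4: clustering.** Absences probably cluster within patients. In a beta-binomial model with within-patient correlation 0.1 to 0.2, P(trigger) is 11–13% at a mean absence of 3%, 19–22% at 5% and 36–43% at 10%. Clustering lowers the higher figures and slightly raises the lowest.

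**Step 5: size of a possible bias.** Suppose no true effect, 23% of one arm excluded, and log-odds of exclusion rising by 0.5 to 1.0 per SD of worse response. That arm's mean change then shifts by about 0.11 to 0.20 SD. This is a shift within one arm. If exclusion is equally frequent and equally response-dependent in two arms, the shifts cancel. With 18% excluded in one arm and 28% in the other, the net between-arm bias is about 0.05 to 0.08 SD.

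**The case against.** The strongest defence is that the protocol never says these patients are excluded. The rule speaks only of consideration, assessments are planned for baseline and week 6 without any attendance condition, and a patient who attended 16 of 18 sessions can supply a week-6 value. The ANOVA's need for both values would then not remove them. The step from 54 to 60 is a planning margin, not the definition of an analysis set, and a statistical analysis plan that is not shown may keep everyone in. All of this stands, so the point has to be stated as a risk. It does not dispose of the point, because the definition sits in the protocol and governs conduct: if a labelled patient is not brought back at week 6, no later analysis plan recovers the outcome.

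Three stronger readings are tempting and are not supported:

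- *That the rule biases every between-group comparison.* This needs both exclusion and a difference between arms in absence or in its link to response. Neither is stated. The added exercises make longer sessions in arms B and C a fair inference, but the protocol gives a duration only for the core session. Extra burden relative to arm A also gives no reason for a difference between B and C, the comparison posed in the Statement of the Problem.
- *That the allowance is unrealistic.* No absence rate is given. On the consecutive reading, 3% to 5% absence costs only 0.9 to 2.4 patients.
- *That power collapses.* The figure of 0.685 needs 55% of patients to be labelled and excluded. At 5% absence, power stays at about 0.92.

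The choice of missing-data method is properly left to the analysis plan and is not part of this point.

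**Conclusion.** The concern holds in conditional form. The protocol fixes a drop-out definition that depends on attendance, is open to discretion, and is not separated from loss to follow-up, while its sample-size section treats drop-outs as lost. Applied that way, the rule permits selection after randomisation. How much bias follows depends on unknown differences between arms; the illustration in Step 5 runs from zero (similar exclusion in the arms) to about 0.05 to 0.08 SD (18% against 28%).

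The effect on numbers depends on assumed absence rates and on how the rule is read. Counted cumulatively with independent misses, about 3% absence per session uses the allowance of 6 in expectation, and 5% labels about 14 patients. The power figures also rest on r = 0.5 and on every labelled patient being excluded.

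This should be corrected, ideally before patients are enrolled, but it does not invalidate the design.

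**What to change.** In the adherence section, replace the two-absence rule with three statements:

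1. Drop-out means withdrawal of consent or no week-6 assessment.
2. Every randomised patient is invited to the week-6 assessment whatever their attendance, and is analysed in the allocated group.
3. Attendance is reported as an adherence measure and, if wanted, used for a sensitivity analysis labelled as per-protocol.

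The change concerns follow-up and analysis only; it alters no treatment. If attendance alone removes nobody, the six-patient margin is left for true loss to follow-up: power is 0.973 at N = 60 and 0.956 at N = 54 (same assumptions). The cost is a paragraph of text, the effort of bringing irregular attenders back once, and one optional extra analysis. The small downside is that imperfect attenders may slightly dilute the observed effect.

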#### **Treatment Procedures:**

- The control group (n=20) will receive core stabilization (3 sessions/ week for 6 weeks)
- The 1st experimental group (n=20) will receive core stabilization in addition to thoracic mobility exercises (3 sessions/ week for 6 weeks)
- The 2nd experimental group (n=20) will receive core stabilization in addition to hip mobility exercises (3 sessions/ week for 6 weeks).
- Adherence will be monitored using attendance logs and exercise checklists.
- Any adverse effects or symptom exacerbation will be recorded.

#### **A) Core stabilization exercises (control group):**

[figure not shown]
All 3 groups will receive core stabilization exercises based on work of (**Kuzu et al., 2025**). Each exercise session will be performed for approximately 35 minutes with 5 min warm-up.

Before starting the exercise, patients will be taught to reduce the lumbar lordosis by contracting and drawing in the abdominal muscles and to find the

lumbar and pelvic neutral position by moving the pelvis forwards and backwards (pelvic tilt, bridge, bird-dog and plank etc.).

In each session, the neutral position will be found first and attention will be paid to maintain the neutral position throughout the exercise. In addition, core stability exercises including simultaneous contractions of the multifidus and pelvic floor muscles will be given in different positions such as supine, prone, crawling, bridge, kneeling, sitting and standing, as shown in **(figure 7)**. The exercises will consist of 3 levels (from easy to difficult). In the advanced level exercises, patients will be asked to maintain the neutral curvature of the lumbar spine, resistance limb exercises will be added and the exercises will be completed gradually. Each exercise will be performed for 3 sets of 8–10 repetitions, depending on the patient's tolerance.

**Figure (7): Core stabilization exercises (Park & Kim, 2020)**

#### **B) Thoracic Mobility Exercises (1st experimental group only):**

It was developed based on the exercise described by **Henegahn et al., (2020)** and **Choi & Kim, (2023)**, the exercise will consist of movements in all directions of thoracic spine flexion, extension, lateral flexion, and rotation.

In the thoracic spine extension exercise, both hands will be locked behind the wrists and the back will be placed on a foam roller with the feet positioned

[figure not shown]
flat on the floor. The knee will be maintained at 90° to perform the extension exercise on the foam roller, as shown in **(figure 8A)**. Additionally, the hands will be locked with the elbow on a chair. After kneeling, the hip will be moved toward the heels to extend the thoracic spine, as shown in **(figure 8B)**.

In the thoracic spine flexion exercise, the thoracic spine will be flexed by moving backward until the hip touched the heels in a quadruped position, as shown in **(figure 8C)**.

The rotation exercise will be conducted with patients lying on their sides. The elbows will be straight and the palms will be held together. The leg facing the ceiling will be bent to the level of the stomach. Then, the arm facing the ceiling will be moved backward in a large arc to rotate the thoracic spine, as shown in **(figure 8D)**. Another thoracic spine rotation exercise will be conducted as follows in a kneeling position, the hip will touch the heels; the hand in the direction of rotation will be placed behind the neck and the elbow of the opposite arm will be placed on the floor; then, the torso will be slowly rotated toward the ceiling, as shown in **(figure 8E)**.

For lateral flexion of the thoracic spine, both hands will be locked behind the neck with the participant seated on a chair and the torso will be then flexed laterally, as shown in **(figure 8F)**.

[figure not shown]
Each exercise will be performed for 3 sets of 10 repetitions.

**Figure (8): Thoracic Mobility Exercises; A) Thoracic extension with foam roller. (B) Thoracic extension with chair. (C) Thoracic flexion in quadruped position. (D) Thoracic rotation in side lying. (E) Thoracic rotation in a kneeling position. (F) Thoracic lateral flexion in sitting position. (Seo et al., 2022)**

### **C) Hip Mobility Exercises (2nd experimental group only):**

It was conducted based on the exercise described by **Demirtas et al., (2023)** and **Choi & Kim, (2023)**. The patients will perform 8 different hip mobility exercises; reverse v-ups, butterfly, frog, internal rotation with foot rise, pike, revolved crescent lunge, pigeon, lunge on the knee, as shown in **(figure 9)**. Each exercise will be performed for 2 sets of 20 seconds.

**Figure (9): Hip Mobility Exercises. (Demirtas et al., 2023)**

### **Data analysis and statistical design**

Statistical analysis will be performed using SPSS software for Windows, version 25.0 (SPSS, Inc., Chicago, IL) with Alpha level set at 0.05.

- Data will be screened for normality assumption, homogeneity of variance, and presence of extreme scores.
- Descriptive statistics will be calculated for all groups at baseline and after 6 weeks.
- ANOVA, repeated measures, within-between interactions model will be utilized to determine any differences between the mean change scores of groups regarding all outcomes.
- Bonferroni adjusted p-values for every outcome measure to protect against the possibility of type I error.

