### **Assessment Procedures**

All assessments will be conducted at baseline (pre-treatment) and **after 6 weeks** of intervention (post-treatment) by **blinded assessors** to ensure objectivity and minimize bias. Assessment procedures will include:

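### The group comparison uses change scores although baseline values are collected; adjusting week-6 values for baseline would be more precise and would not over-correct chance imbalance

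*Protocol*

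**What the plan says.** Under Data analysis and statistical design, the Protocol names one model for every outcome: "ANOVA, repeated measures, within-between interactions model will be utilized to determine any differences between the mean change scores of groups regarding all outcomes", "with Alpha level set at 0.05". Under Assessment Procedures there are two measurement occasions: "All assessments will be conducted at baseline (pre-treatment) and after 6 weeks of intervention (post-treatment". The Sample Size Calculation uses the same test: "A priori power analysis for ANOVA, repeated measures, within-between interactions was used with an effect size of 0.28", with power 0.95. It continues: "The estimated sample size required was 54 participants, which was increased to account for potential dropouts", so that "the total sample will include 60 participants, randomly allocated into 3 equal groups (n= 20 per group".

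The Protocol mentions no baseline covariate. The Participants section describes allocation by a web randomiser, with no stratification or other balancing on baseline values. The choice of model is thus fixed in the Protocol itself and is not left open for a later document.

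**The concern.** With two time points, the group-by-time interaction in a repeated-measures ANOVA is algebraically the one-way ANOVA of (week 6 minus baseline). A change score takes off the whole of the baseline value, which imposes a slope of 1 in the regression of week 6 on baseline. When the two variances are equal, the true slope is r. For r below 1 this has two consequences:

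- The treatment contrast has a larger variance than it needs.
- If the arms differ at baseline by chance, the contrast moves too far in the opposite direction, so the arm that starts worse appears to improve more.

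The stake is greatest for the question under Statement of the Problem, namely which of the two add-ons is superior. That is a pairwise contrast with 20 patients per arm, whereas the sample size was set for the three-group interaction test.

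**Working it through.** **Inputs.** From the Protocol: 3 groups, 2 measurements, f = 0.28, alpha 0.05, power 0.95, N = 54 before dropout, 60 in total, 20 per arm. Assumed: the correlation r (not in the readable text, and Figure 1 is not shown), equal variances at both times, and, for the pairwise illustration, a difference of 0.8 SD at alpha 0.05/3.

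**1. Reproducing N = 54.** For the within-between interaction, lambda = f² × N × 2/(1-r), with 2 and N-3 degrees of freedom.
- r = 0.5: lambda = 0.28² × 2/0.5 × N = 0.3136 N. At N = 54, lambda = 16.93 and power is 0.956. At N = 51 power is 0.944. The smallest balanced N is therefore 54, as planned.
- r = 0, 0.3 and 0.7 would give 102, 75 and 33. The assumed 0.5 fits the stated figure and these alternatives do not.

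**2. Precision.** With common SD s:
- Var(change) = 2s²(1-r)
- Var(ANCOVA) = s²(1-r²)
- Ratio = (1-r²)/[2(1-r)] = (1+r)/2

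The ratio is 0.65, 0.75 and 0.85 at r = 0.3, 0.5 and 0.7, so the SE is smaller by 19.4%, 13.4% and 7.8%. A simulation of 20,000 trials with 20 per arm at r = 0.5 gave a ratio of 0.763. The slight excess over 0.75 is the cost of estimating the slope.

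**3. Omnibus power at r = 0.5.** The ANCOVA lambda is 0.3136/0.75 × 54 = 22.58, with 2 and 50 degrees of freedom. Power at N = 54 is 0.990, against 0.956. At N = 60 with all patients completing, it is 0.995 against 0.973. Under ANCOVA, 42 patients would reach 0.95.

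**4. Pairwise power, 0.8 SD, alpha 0.05/3, 20 per arm.** Noncentral t, with noncentrality 0.8/SE and SE² = (2/20) × the variance above in SD units. Residual degrees of freedom are 57 (change) and 56 (ANCOVA).

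| r | SE change | SE ANCOVA | Power change | Power ANCOVA |
|---|---|---|---|---|
| 0.3 | 0.374 | 0.302 | 0.38 | 0.58 |
| 0.5 | 0.316 | 0.274 | 0.53 | 0.67 |
| 0.7 | 0.245 | 0.226 | 0.79 | 0.85 |
| 0.9 | 0.141 | 0.138 | above 0.99 | above 0.99 |

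**5. Chance imbalance.** The SE of a baseline difference between two arms is sqrt(2/20) = 0.316 SD. For a given pair, P(gap above 0.5 SD) = 2 × [1 - Φ(0.5/0.316)] = 0.114. For at least one of the three pairs, the studentized range gives 0.254. Given a gap d, the change-score contrast shifts by (r-1)d. At d = 0.5 and r = 0.5 this is -0.25 SD, the same size as the shift with no adjustment at all (r × d = +0.25 SD) but opposite in sign. In the simulation the change-score estimate correlated -0.50 with the baseline gap, and the ANCOVA estimate 0.00.

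**The case against.** The planned test is a legitimate one. Under randomisation it is unbiased on average and holds its type I error, and the variability due to baseline imbalance is already in its standard error. The 0.25 SD shift in the example is smaller than one SE (0.316 SD) of the contrast. The analysis matches the sample-size calculation, and on the Protocol's own inputs, with r = 0.5, omnibus power at 60 is 0.973. All of this stands. It makes the point one of efficiency and of sensitivity to the imbalance that actually occurs.

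The gain also depends on r. The value 0.5 is inferred from the pain calculation and says nothing about the other outcomes. The Protocol cites ICCs of 0.89 to 0.98 for the BROM device and the Schober test. If that reliability carried over into a high baseline to week-6 correlation, the gain for those outcomes would be small. The formulas further assume equal variances at both times; otherwise the true slope is r times the ratio of the SDs, and the size of the gain changes. The 0.8 SD and 0.05/3 in the pairwise illustration are not in the Protocol, whose Bonferroni line does not spell out a division by three pairs.

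A reader might infer that change scores leave baseline imbalance uncorrected. They do not: they subtract baseline in full, which is too much when r is below 1. A reader might also infer that the entry requirement of an NPRS above 3 will produce a spurious treatment effect through regression to the mean. Selection at entry acts alike on all randomised arms, so by itself it creates no difference between them; it concerns one outcome only, and matters only where the arms happen to differ at baseline.

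**Conclusion.** The point holds as a recommended improvement. The Protocol fixes an analysis that is valid but, for r below 1, less precise than one using the same data with baseline as a covariate, and that over-corrects chance imbalance by (1-r) times the gap. Under the assumed r = 0.5 the variance is a third larger than necessary (1/0.75 = 1.33), and the illustrative pairwise power is 0.53 where 0.67 is available. Between r = 0.3 and r = 0.7 the pairwise gain runs from about 20 to about 6 percentage points, and it is negligible at r = 0.9. The chance of a baseline gap above 0.5 SD is about 11% for a named comparison such as thoracic versus hip; the 25% figure applies to any of the three pairs and should not be read as the risk for one of them.

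The documents do not support the stronger conclusions that the trial will have an inflated false-positive rate, that its omnibus test is underpowered on its own assumptions, or that 60 patients is the wrong number.

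**What to change.** In Data analysis and statistical design, make the main analysis of each outcome an ANCOVA of the week-6 value on group, with that outcome's baseline value as covariate. Report adjusted pairwise mean differences with 95% confidence intervals. Keep the repeated-measures interaction test as a sensitivity analysis, which preserves the link to the sample-size calculation.

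The change should be made before outcome data are seen, so that the choice of model cannot appear data-driven. It costs a few lines of text. Baseline values are already collected for every outcome, the named software can fit the model, and no extra patients or visits are needed.

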### **Statement of the Problem**

Which modality is superior when combined with core stabilization for treating individuals with lumbar spondylosis in terms of outcomes: thoracic mobility exercises or hip mobility exercises with regard to severity of pain, disability function, range of motion at the lumbar spine (flexion, extension, lateral flexion, and rotation), spinal mobility, quality of life, and fear of movement?

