### **Hypotheses**

1. There will be no significant difference between core stabilization, core stabilization with thoracic mobility exercises, and core stabilization with hip mobility exercises on **pain severity** in participants with lumbar spondylosis.
2. There will be no significant difference between core stabilization, core stabilization with thoracic mobility exercises, and core stabilization with hip mobility exercises on **functional disability** in participants with lumbar spondylosis.
3. There will be no significant difference between core stabilization, core stabilization with thoracic mobility exercises, and core stabilization with hip mobility exercises on **lumbar flexion range of motion** in participants with lumbar spondylosis.
4. There will be no significant difference between core stabilization, core stabilization with thoracic mobility exercises, and core stabilization with hip mobility exercises on **lumbar extension range of motion** in participants with lumbar spondylosis.
5. There will be no significant difference between core stabilization, core stabilization with thoracic mobility exercises, and core stabilization with hip mobility exercises on **lumbar right lateral flexion range of motion** in participants with lumbar spondylosis.
6. There will be no significant difference between core stabilization, core stabilization with thoracic mobility exercises, and core stabilization with hip mobility exercises on **lumbar left lateral flexion range of motion** in participants with lumbar spondylosis.
7. There will be no significant difference between core stabilization, core stabilization with thoracic mobility exercises, and core stabilization with hip mobility exercises on **lumbar right rotation range of motion** in participants with lumbar spondylosis.
8. There will be no significant difference between core stabilization, core stabilization with thoracic mobility exercises, and core stabilization with hip mobility exercises on **lumbar left rotation range of motion** in participants with lumbar spondylosis.

9. There will be no significant difference between core stabilization, core stabilization with thoracic mobility exercises, and core stabilization with hip mobility exercises on **spinal mobility** in participants with lumbar spondylosis.

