10. There will be no significant difference between core stabilization, core stabilization with thoracic mobility exercises, and core stabilization with hip mobility exercises on **quality of life** in participants with lumbar spondylosis.
11. There will be no significant difference between core stabilization, core stabilization with thoracic mobility exercises, and core stabilization with hip mobility exercises on **fear of movement** in participants with lumbar spondylosis.

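### No primary outcome is named for eleven parallel hypotheses, and the Bonferroni rule has no divisor; on either reading the plan misses its stated error rate or its stated power

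*Protocol*

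**What the plan says.** The Statement of the Problem in Chapter I asks "Which modality is superior when combined with core stabilization for treating individuals with lumbar spondylosis in terms of outcomes" and then lists pain, disability, lumbar range of motion, spinal mobility, quality of life and fear of movement side by side. The Hypotheses section turns this into eleven null hypotheses of the same form. They start with pain and disability and run through six separate range-of-motion directions (for example "core stabilization with hip mobility exercises on lumbar left rotation range of motion in participants with lumbar spondylosis") to spinal mobility, quality of life and "core stabilization with hip mobility exercises on fear of movement in participants with lumbar spondylosis". None is marked primary, secondary or exploratory.

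In Chapter III, Sample Size Calculation gives a power analysis that "was used with an effect size of 0.28", alpha 0.05 and power 0.95, leading to 54 patients, raised to 60 for dropout. The effect size comes from one outcome: "referencing effect size data of pain severity from a recent study".

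Data analysis and statistical design analyses the data "with Alpha level set at 0.05", using the group-by-time ANOVA "to determine any differences between the mean change scores of groups regarding all outcomes". Multiplicity is covered by one line: "Bonferroni adjusted p-values for every outcome measure to protect against the possibility of type I error". The divisor is not given.

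**The concern.** The Bonferroni line can be read in two ways. It may correct the three pairwise group comparisons inside each outcome, which leaves each of the eleven outcomes with its own full 0.05. Or it may divide alpha across the eleven outcomes, which gives pain the same small share as left rotation, although the trial was sized for pain at 0.05.

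The choice can change the conclusion. An omnibus p of 0.02 on any outcome is significant on the first reading (0.02 < 0.05) and not on the second (0.02 > 0.05/11 = 0.0045). Nothing says which outcome decides the superiority question if outcomes disagree. Seven of the eleven hypotheses concern movement range (six directions plus the Schober test). If the deciding outcome or the divisor is chosen after the data are seen, the results can steer the choice.

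**Working it through.** **Inputs from the protocol.** Three groups of 20; two measurements (baseline and 6 weeks, Assessment Procedures); effect size f = 0.28; alpha 0.05; power 0.95; N = 54 before dropout; eleven hypotheses.

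**Assumed, because not given.** Pre-post correlation ρ for the power calculation, sphericity (automatic with two time points), and a common correlation r between the outcomes' change scores.

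**Step 1: reproduce the sample size.** For the within-between interaction with k = 3 groups and m = 2 measurements:

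- λ = N f² m / (1 − ρ), df1 = (k − 1)(m − 1) = 2, df2 = (N − k)(m − 1) = N − 3.
- With N = 54 and ρ = 0.5: λ = 54 × 0.0784 × 2 / 0.5 = 16.93, df2 = 51.
- Power at alpha 0.05 is 0.944 for N = 51, 0.956 for N = 54 and 0.973 for N = 60.

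The stated 54 is reproduced. The required N would be 102, 75 and 33 at ρ = 0, 0.3 and 0.7, so of the values tried only 0.5 returns 54. The calculation is for one test at undivided 0.05.

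**Step 2: Bonferroni within each outcome only.** With two time points the interaction test equals a one-way ANOVA on change scores, F(2, 57). For independent outcomes the chance of at least one false omnibus result is 1 − 0.95¹¹ = 0.431. For correlated outcomes it was simulated with no group effects (3 × 20 patients, eleven normal change scores, 20,000 runs per row, 60,000 at r = 0.5). Each entry is the chance of at least one significant result:

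| r | Omnibus F at 0.05 | Any pair at 0.05/3 | Thoracic v hip only at 0.05/3 | Omnibus F at 0.05/11 |
|---|---|---|---|---|
| 0 | 0.431 | 0.388 | 0.170 | 0.051 |
| 0.3 | 0.383 | 0.342 | 0.148 | 0.047 |
| 0.5 | 0.312 | 0.281 | 0.122 | 0.039 |
| 0.7 | 0.233 | 0.209 | 0.089 | 0.031 |
| 0.8 | 0.193 | 0.172 | 0.075 | 0.025 |
| 0.9 | 0.138 | 0.124 | 0.055 | 0.020 |

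The 0.051 in the last column is simulation noise, since Bonferroni bounds it at 0.05. Two block structures, with higher correlation among the movement measures and among the questionnaires than between the two sets, gave 0.323 and 0.359 (omnibus) and 0.290 and 0.323 (any pair).

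**Step 3: Bonferroni across the eleven outcomes.** The threshold is 0.05/11 = 0.0045. With f = 0.28 and ρ = 0.5 as in Step 1, power is 0.775 at N = 54 and 0.838 at N = 60. About 81 patients would be needed for 0.95.

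**Step 4: one primary outcome.** With pain alone tested at 0.05, the error for the main claim is 0.05 and Step 1 applies unchanged: power 0.956 with 54 patients.

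**The case against.** The strongest objection is that the inflation belongs to one reading of an ambiguous sentence. The line says its purpose is to guard against type I error, and adjusting across outcomes is a fair reading; on it the error is controlled. That stands for the error rate. It moves the problem to power, because the sample size was set at undivided 0.05.

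A reader might infer that the plan's false-positive rate simply is about 0.3. The documents do not support that. The figure needs the within-outcome reading and an assumed r of 0.5, and it counts any arm differing from any other in either direction. An omnibus F names no better arm. For the thoracic-versus-hip question alone the figure is about 0.12 at r = 0.5, and close to 0.05 at r = 0.9.

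A reader might also infer a rule that one significant outcome out of eleven makes an add-on superior. No such rule is written. The hypotheses are outcome-specific and could lead to outcome-specific conclusions; the protocol says nothing either way. Nor does the p = 0.02 example carry over to a raw pairwise p, which would fail both 0.05/3 = 0.0167 and 0.0045.

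Finally, pain comes first in every list and sizes the trial, front pages were not available, and an unseen SAP might give the divisor. Pain may well be the intended primary outcome, but the available text does not say so. Choosing the deciding outcome belongs in the protocol, and the protocol's own multiplicity line and sample size conflict on one of the two readings.

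**Conclusion.** The point holds in a conditional form. No outcome is named primary in the text available, and the Bonferroni line does not fix its divisor. Neither reading gives both the error control and the power that the protocol states:

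- **Within-outcome reading:** the chance of at least one false finding is about 0.17 to 0.43 for r from 0.8 to 0, and still 0.12 to 0.14 at r = 0.9. For thoracic versus hip alone it is about 0.05 to 0.17 over r from 0.9 to 0.
- **Across-outcome reading:** the error is at most 0.05, but power is 0.775 (N = 54) or 0.838 (N = 60) instead of 0.95.

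The error figures rest on assumed correlations and normal change scores. The power figures rest on a pre-post correlation of 0.5, the value that reproduces the stated sample size. The count of eleven may be low: the protocol describes eight SF-36 domains and two summary scores and does not say which one tests the quality-of-life hypothesis.

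**What to change.** Before data are seen, amend the Hypotheses and Data analysis and statistical design sections as follows:

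- Name pain severity (NPRS-Ar, change from baseline to week 6) as the single primary outcome, tested at 0.05, and rest the trial's main conclusion on it.
- Label hypotheses 2 to 11 secondary, with Holm adjustment across the ten. This needs one SF-36 score named for hypothesis 10.
- Replace the Bonferroni line with a statement that Bonferroni with divisor 3 applies to the pairwise group comparisons within an outcome.

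The cost is a few sentences, with no added patients, visits or measurements, and the stated power is kept. The downside is that a positive result on a secondary outcome alone no longer supports the main superiority claim. If the sponsor instead wants all eleven outcomes to count equally, the division by eleven should be written down and the sample size redone, at about 81 patients before dropout on the assumptions above.
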